**Methods:**

Objective determination of levels of physical activity, sedentary lifestyle and sleep quality: accelerometry

The accelerometer used was the Actigraph wGT3X-BT, which is a small and light triaxial accelerometer (4.6 x 3.3 x 1.5 cm, 19 g) with a response frequency of 30 to 100 hertz. This device was used to measure different objective parameters such as physical activity and its intensity, energy expenditure, metabolic equivalents rhythms (MET), weekly steps, sedentary bouts and sleep latency and efficiency. Participants wore the accelerometer held with an elastic band on the non-dominant wrist for 7 consecutive days and without interruption, except for those times of the day in which the correct operation of the device could be compromised (showers or any activity related to water). Subsequently, the files generated by the accelerometer were analyzed through a specific software called Actilife 6 (Actigraph, Pensacola, USA).

Determination of perceived levels of general health, stress, anxiety, fatigue, depression and sleep quality: questionnaires

Participants had to fill out a series of validated questionnaires to identify possible subjective health and mental states.

SF-36 Questionnaire. This is an instrument that provides results about the health status of a general population covering 8 scales: physical function, physical role, body pain, general health, vitality, social role, emotional role and mental health. The scales are ordered so that the higher the score, the better the health status (0 to 100).

Sleep Quality in Healthy Lifestyle and Personal Control Questionnaire (HLPCQ). The HLPCQ is a questionnaire whose main objective is to detect and quantify lifestyle patterns that reflect health empowerment, as evidenced by the levels of stress and of the internal locus of control. It also includes a section with various questions to measure sleep quality where higher scores indicate better sleep quality.

The State-Trait Anxiety Inventory (STAI). This questionnaire analyzes the degree of anxiety that each participant shows. It is divided into two parts: trait-anxiety (what they usually or generally felt) and state-anxiety (their expressed emotions at a specific moment), in which higher scores indicate a higher state of anxiety.

The Perceived Stress Scale (PSS). This questionnaire allowed the frequency at which individuals had experienced certain stressful feelings to be assessed, as well as their thoughts in the last month.

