### **Statistical Analysis Plan (SAP):**

Statistical analysis was performed with IBM statistics SPSS v20.0 software (SPSS Inc., Chicago IL, USA). To verify the normality of the data, the Shapiro-Wilk test was performed. The repeated two-way analysis of variance (ANOVA) was used, followed by Student's paired and unpaired t-tests to analyze the intervention effect. The values were expressed as mean  $\pm$  standard deviation (SD) and the significance level was considered when  $p<0,05$ .

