### Results:

Among the most important results we can observe:

the sedentary group administered with placebo obtained some significant differences with respect to baseline values ( $p<0,05$ ). A decrease in calories, metabolic rate and intensity level of physical activity are reflected. The synbiotic seems to prevent this situation by avoiding the mentioned decreases and even increasing the consumption of Kilocalorie (Kcal) in sedentary individuals although without significant differences. Results from the athlete group show no significant changes ( $p>0,05$ ) in those who consumed placebo, while those who followed the protocol with the intake of the synbiotic had significant improvements in sleep efficiency and latency, as well as increases in the consumption of Kcal and METS.

The baseline values are quite similar in the sedentary and athlete groups. Only in the athletes did the synbiotic intervention significantly improve ( $p<0,05$ ) the perceived general health as determined by the SF-36 questionnaire, but no differences were found in perceived sleep quality, state anxiety, and fatigue.

No significant differences were found in the perceived stress, trait anxiety, and depression between sedentary people and athletes at basal status (before intervention). The results show a decrease in the levels of perceived stress ( $p<0.01$ ) and anxiety ( $p<0.05$ ) only in the athlete group administered with the synbiotic. Also shows a decrease ( $p<0.05$ ) in perceived depression levels in both groups (sedentary and athlete) after the synbiotic treatment. Then, training only affected the behavior in response to the synbiotic intervention in stress and particularly in anxiety ( $p<0.05$ ) also when evaluating by the two way ANOVA test). These effects were not due to a placebo effect.

The results corresponding to blood concentrations of glucose, cholesterol, and triglycerides as measurements of metabolic profile. Firstly, individuals in both the sedentary and athlete groups presented lipid and glycaemic levels compatible with normal and healthy ranges. Thus, as expected the consumption of the synbiotic did not provoke an appreciable or significant effect

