It should be noted that both groups presented healthy baseline levels of the inflammatory and immune parameters analysed. No significant differences in the IL-1 $\beta$  concentrations were observed between the sedentary and athlete groups. However, a different behaviour ( $p<0.05$ ) between the two groups was found in response to the synbiotic intervention: while the synbiotic increased ( $p<0.05$ ) the systemic concentration of IL-1 $\beta$  in the sedentary group, it slightly decreased in the soccer player group.

No significant variations (except a potential placebo effect in the sedentary group) were found in the IL-10 concentration. There were also no significant differences in the levels of immunoglobulin A between groups, or as a consequence of the intervention.

A lower concentration without significant differences were found in the dopamine concentration of the soccer players group. However, training affected the response to the synbiotic intervention ( $p<0.05$ ), since it induced a significant increase ( $p<0.05$ ) in the dopamine concentration only in the athletes. This effect cannot be attributable to a potential placebo effect of the intervention. However, the decrease ( $p<0.05$ ) in epinephrine levels in the sedentary group administered with the synbiotic compared to their basal levels could potentially be attributed to a placebo effect of the intervention. In addition, there were also no significant changes in norepinephrine. Basal concentration of serotonin was, however, higher ( $p<0.05$ ) in the athlete group than in the sedentary group, but statistical differences with the synbiotic intervention were not observed.

Finally, the results corresponding to CRH showed a lower systemic concentration of CRH than sedentary volunteers. In addition, the behaviour of CRH secretion in response to the synbiotic intervention was also different ( $p<0.05$ ) between the athlete group and the sedentary group, decreasing significantly ( $p<0.05$ ) in the sedentary group with respect to their baseline levels (as also found with the placebo) and increasing slightly in the athlete group. The latter cannot be attributable to a placebo effect of the intervention. There were no significant differences in levels of cortisol and ACTH between groups or as a consequence of the intervention.

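### Results rule out a placebo effect in three places, but none of the 15 reported p-values is attached to a synbiotic-versus-placebo comparison

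*Combined protocol and SAP*

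**What the plan says.** The SAP section is one paragraph. It gives a Shapiro-Wilk check, a two-way repeated ANOVA and then paired and unpaired t-tests as the means of analysing the intervention effect. It does not say which two factors enter the ANOVA, which contrasts the t-tests address, or whether a t-test was run only after a significant ANOVA term. Its sole decision rule is that "the significance level was considered when" p was below 0.05. No section names a primary outcome or a multiplicity rule.

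Results draws three firm conclusions about placebo:

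- After the stress, anxiety and depression findings: "These effects were not due to a placebo effect". The sentence clearly covers stress and anxiety and may also cover depression.
- After the dopamine rise in athletes: "This effect cannot be attributable to a potential placebo effect of the intervention".
- After CRH, which fell in sedentary people and rose slightly in athletes: "The latter cannot be attributable to a placebo effect of the intervention". The rise in athletes has no p-value of its own.

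Elsewhere the text is more cautious. The sedentary epinephrine fall on synbiotic "could potentially be attributed to a placebo effect of the intervention". The CRH fall occurred "in the sedentary group with respect to their baseline levels (as also found with the placebo".

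**The concern.** Randomisation to synbiotic or placebo is what lets this trial separate the supplement from everything else that happened over 30 days. A before-after test within one cell does not use it. Such a test picks up any change over time, and the Design section says that the period coincided with the end of exams and the end of the soccer season, times of possible physical and mental stress. Stress, anxiety and stress hormones are outcomes that could move for that reason alone.

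Comparing the responses of athletes and sedentary people does not repair this. Membership of those groups was not randomised, and each faced its own source of stress, so different responses could reflect different time trends.

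At stake is whether the psychological and hormonal effects can be credited to the supplement. A reader who accepts the three placebo sentences would take them as results of a controlled comparison, which the supplied text does not show.

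**Working it through.** The documents state no sample size, power or count of tests, so there is no figure of theirs to reproduce. The check is a count, followed by one illustration.

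**1. The p-value statements in Results.**

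| Type of comparison | Findings | Count |
|---|---|---|
| Before-after, synbiotic cell | Athletes: SF-36 health, stress, anxiety, dopamine. Both populations: depression. Sedentary: IL-1β, epinephrine, CRH | 8 |
| Before-after, placebo cell | Accelerometry: sedentary (p<0.05), athletes (p>0.05) | 2 |
| Athlete versus sedentary response | Stress/anxiety (two-way ANOVA), IL-1β, dopamine, CRH | 4 |
| Athlete versus sedentary at baseline | Serotonin | 1 |
| Synbiotic versus placebo | None | 0 |

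Total: 8 + 2 + 4 + 1 + 0 = 15. By threshold, 13 are p<0.05, one is p<0.01 (stress) and one is p>0.05. No exact p-value, between-arm estimate or interval is printed.

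**2. The three placebo sentences set against that table.** For stress and anxiety, the p-values are before-after within the athlete synbiotic cell, plus an ANOVA result worded as an effect of training. For dopamine, they are one before-after change and one athlete-versus-sedentary comparison. For CRH in athletes, there is only the comparison with sedentary people. None of the three is accompanied by a between-arm number.

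**3. Why significant on one arm only is not a test.** Let each arm's mean change have the same standard error, SE, with independent arms. The difference between arms then has standard error √2 × SE, so

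z(between) = (z(synbiotic) − z(placebo)) / √2.

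The z-values are assumed and the p-values two-sided:

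- z of 2.0 (p = 0.046) and 1.0 (p = 0.32): (2.0 − 1.0)/1.414 = 0.71, p = 0.48.
- z of 2.0 and 0.0: 2.0/1.414 = 1.41, p = 0.16.
- z of 2.58 (p = 0.01) and 0.0: 2.58/1.414 = 1.82, p = 0.07.

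So even a within-arm p of 0.01, set beside no change at all on placebo, need not give a between-arm p below 0.05.

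**4. Evidence within the trial.** Sedentary CRH fell on both arms, and the text itself allows that the sedentary epinephrine fall may be a placebo effect. Before-after significance on synbiotic therefore did not isolate the supplement in at least one outcome, and possibly in two.

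**5. Secondary count: outcomes.** Accelerometry 8 (activity, its intensity, energy expenditure, METs, steps, sedentary bouts, sleep latency, sleep efficiency); questionnaires 7 (SF-36, HLPCQ sleep, STAI state, STAI trait, PSS, BFI, BDI); metabolic 3; immune and neuroendocrine 10. Sum: 8 + 7 + 3 + 10 = 28. SF-36 is described as "covering 8 scales: physical function, physical role, body pain, general health, vitality, social role, emotional role and mental health"; counting these separately gives 28 + 7 = 35. As an illustration only, one test per outcome with no true change would give 28 × 0.05 = 1.4 chance findings. The number of tests actually run is not stated.

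**The case against.** The strongest reply is that the fault may lie in reporting and not in analysis. The SAP does include unpaired t-tests and an ANOVA for the intervention effect, in a placebo-controlled design. The ANOVA factors are unnamed, so a treatment term behind the anxiety p-value cannot be fully excluded, although that sentence is about training. Results begins with "Among the most important results we can observe", so it is a selection. This stands: a reader might infer that no between-arm analysis was ever done, and the documents do not support that. They support only that none is shown.

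A second reply is that the study is a pilot looking for possible effects, where unadjusted testing of many outcomes is ordinary. This also stands as regards multiplicity. A reader might go further and infer that the significant results are mostly chance findings from many tests. That would need the number of tests run and the number significant, and the text establishes neither: it does not say that paired tests were run in all four cells for every outcome, and it mentions some significant differences in the sedentary placebo cell without giving each its own p-value. Pilot status does not, however, cover a statement that a placebo effect has been excluded.

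A third reply is that many changes in athletes on synbiotic and none on placebo would be indirect evidence of a difference between arms. That has some force in principle. But the statement of no significant change in athletes on placebo sits with the accelerometry results. For questionnaires and hormones in that cell the supplied text prints no numerical result, and even a clear overall pattern would not validate any single outcome.

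**Conclusion.** The concern holds as a gap between the reported tests and the conclusions drawn from them. The size is 0 of 15 p-value statements attached to the randomised comparison, against three sentences excluding a placebo effect. The count depends on reading the one ANOVA statement as a comparison of populations, which its wording favours but does not settle. The 0.48 figure is an illustration under equal standard errors and independent arms; it is not an estimate for any outcome in this trial.

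It does not follow that the effects are placebo effects, or that the synbiotic does nothing. The supplied text cannot settle either question for any individual outcome. The absence of a primary outcome and of a multiplicity rule across about 28 outcomes is secondary: acceptable in a pilot, provided that the results are presented as exploratory. The point should be addressed before the efficacy statements are relied on.

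**What to change.** 1. For every listed outcome, report the synbiotic-minus-placebo difference in change within each population, and the treatment-by-population interaction, each with an exact p-value and 95% confidence interval. With 28 outcomes this is 28 × 2 = 56 differences and 28 interactions (70 and 35 if the SF-36 scales are separate). Base conclusions about the synbiotic on these, with within-arm changes as description only.
2. In the SAP, name the two ANOVA factors and the t-test contrasts used, and say whether the t-tests were conditional on the ANOVA. State whether the SF-36 result is one scale or a summary.
3. Remove or soften each of the three placebo sentences wherever the between-arm difference does not support it.
4. Label all outcome results exploratory. False-discovery q-values may be added as a guide. Do not name a primary outcome after the fact.

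The cost is a reanalysis of existing data and revised wording, with no new data; if the between-arm analyses already exist, it is less. The downside is that fewer results may be called significant and that the between-arm intervals may be wide in a pilot.

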### Results:

Among the most important results we can observe:

the sedentary group administered with placebo obtained some significant differences with respect to baseline values ( $p<0,05$ ). A decrease in calories, metabolic rate and intensity level of physical activity are reflected. The synbiotic seems to prevent this situation by avoiding the mentioned decreases and even increasing the consumption of Kilocalorie (Kcal) in sedentary individuals although without significant differences. Results from the athlete group show no significant changes ( $p>0,05$ ) in those who consumed placebo, while those who followed the protocol with the intake of the synbiotic had significant improvements in sleep efficiency and latency, as well as increases in the consumption of Kcal and METS.

The baseline values are quite similar in the sedentary and athlete groups. Only in the athletes did the synbiotic intervention significantly improve ( $p<0,05$ ) the perceived general health as determined by the SF-36 questionnaire, but no differences were found in perceived sleep quality, state anxiety, and fatigue.

No significant differences were found in the perceived stress, trait anxiety, and depression between sedentary people and athletes at basal status (before intervention). The results show a decrease in the levels of perceived stress ( $p<0.01$ ) and anxiety ( $p<0.05$ ) only in the athlete group administered with the synbiotic. Also shows a decrease ( $p<0.05$ ) in perceived depression levels in both groups (sedentary and athlete) after the synbiotic treatment. Then, training only affected the behavior in response to the synbiotic intervention in stress and particularly in anxiety ( $p<0.05$ ) also when evaluating by the two way ANOVA test). These effects were not due to a placebo effect.

The results corresponding to blood concentrations of glucose, cholesterol, and triglycerides as measurements of metabolic profile. Firstly, individuals in both the sedentary and athlete groups presented lipid and glycaemic levels compatible with normal and healthy ranges. Thus, as expected the consumption of the synbiotic did not provoke an appreciable or significant effect

It should be noted that both groups presented healthy baseline levels of the inflammatory and immune parameters analysed. No significant differences in the IL-1 $\beta$  concentrations were observed between the sedentary and athlete groups. However, a different behaviour ( $p<0.05$ ) between the two groups was found in response to the synbiotic intervention: while the synbiotic increased ( $p<0.05$ ) the systemic concentration of IL-1 $\beta$  in the sedentary group, it slightly decreased in the soccer player group.

No significant variations (except a potential placebo effect in the sedentary group) were found in the IL-10 concentration. There were also no significant differences in the levels of immunoglobulin A between groups, or as a consequence of the intervention.

A lower concentration without significant differences were found in the dopamine concentration of the soccer players group. However, training affected the response to the synbiotic intervention ( $p<0.05$ ), since it induced a significant increase ( $p<0.05$ ) in the dopamine concentration only in the athletes. This effect cannot be attributable to a potential placebo effect of the intervention. However, the decrease ( $p<0.05$ ) in epinephrine levels in the sedentary group administered with the synbiotic compared to their basal levels could potentially be attributed to a placebo effect of the intervention. In addition, there were also no significant changes in norepinephrine. Basal concentration of serotonin was, however, higher ( $p<0.05$ ) in the athlete group than in the sedentary group, but statistical differences with the synbiotic intervention were not observed.

Finally, the results corresponding to CRH showed a lower systemic concentration of CRH than sedentary volunteers. In addition, the behaviour of CRH secretion in response to the synbiotic intervention was also different ( $p<0.05$ ) between the athlete group and the sedentary group, decreasing significantly ( $p<0.05$ ) in the sedentary group with respect to their baseline levels (as also found with the placebo) and increasing slightly in the athlete group. The latter cannot be attributable to a placebo effect of the intervention. There were no significant differences in levels of cortisol and ACTH between groups or as a consequence of the intervention.

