**Objective:**

The main objective of this research was to carry out an experimental study, triple blind, on the possible immunophysiological effects of a nutritional supplement (Synbiotic, Gasteel Plus®, Heel España S.A.U.), containing a mixture of probiotic strains, such as *Bifidobacterium lactis* CBP-001010, *Lactobacillus rhamnosus* CNCM I-4036, *Bifidobacterium longum* ES1, as well as prebiotic fructooligosaccharides, in both professional athletes and sedentary people.

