**Design:**

This investigation was a triple blinded, randomized, placebo-controlled pilot study designed to identify the possible differing effects of the synbiotic Gasteel Plus® supplementation between sedentary individuals and soccer players. Subjects were asked to maintain their regular lifestyle and the participants were prohibited from consuming probiotics, prebiotics or fermented products (yogurt or other foods) to avoid unnecessary interference during the experimental periods. Presenting injury or illness would result in exclusion from the study. All participants were also asked to provide written informed consent before participating in the study, which had been previously approved by the ethics committee of the Catholic University of Murcia (Spain) following current legislation (CE031810).

On two separate days, the "baseline-tests" and "final-tests" were conducted. All participants performed a series of tests, before which they had to fast. The order and schedule (8 am) of the tests was the same for the "final-test" and the same materials and procedures were used. A period of 30 consecutive days elapsed between the base-line and final tests, during which the participants had to ingest their supplement (synbiotic or placebo). Accelerometers were distributed one week prior to the baseline test and the week after the final test. Blood and saliva sampling were taken early in the morning and questionnaires were filled out on the two testing days. The treatment was carried out during the last fortnight of May 2019 and the first fortnight of June of the same year, coinciding with situations of possible physical and mental stress in both participant groups, being at the end of an examination period, as well as the end of the soccer season.

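### The SAP specifies no overall synbiotic-minus-placebo contrast adjusted for population, and the Results give none; it should be reported beside the population-specific contrasts and the interaction

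*Combined protocol and SAP*

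**What the plan says.** The Objective section asks about effects "in both professional athletes and sedentary people". The Design section describes a randomised, placebo-controlled pilot "designed to identify the possible differing effects of the synbiotic Gasteel Plus® supplementation between sedentary individuals and soccer players". Results mentions placebo recipients among both sedentary people and athletes, so the layout is population by arm.

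The SAP's account of the main analysis is one sentence: "The repeated two-way analysis of variance (ANOVA) was used, followed by Student's paired and unpaired t-tests to analyze the intervention effect". The threshold is p below 0.05. The two ANOVA factors, the contrast that represents the intervention effect and any rule for combining the populations are not stated.

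The Results section gives positive findings separately for each population, mostly as change from baseline in one arm. Where it cites the ANOVA, the question is whether training altered the response to the synbiotic. For depression it reports a fall "in perceived depression levels in both groups (sedentary and athlete) after the synbiotic treatment". It says that the effects in that paragraph are not placebo effects, but shows no synbiotic-minus-placebo difference. Null findings are given as statements about significance, for example "There were no significant differences in levels of cortisol and ACTH between groups or as a consequence of the intervention".

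**The concern.** Both populations have a randomised comparison with placebo, so a synbiotic-minus-placebo effect averaged over them can be estimated from data already in hand. It is one natural answer to the Objective and the most precise estimate against placebo if the two populations respond alike. Nothing in the SAP or Results lets a reader find it.

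Two kinds of conclusion suffer. A shared effect, such as the one suggested for depression, is described by two separate tests and never estimated once. A null finding (cortisol, ACTH, IgA, norepinephrine, metabolic profile) comes with no estimate or interval, so the reader cannot tell what size of effect has been excluded. Separate small tests can also make a shared effect look specific to one population.

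**Working it through.** **Inputs.** The documents give no sample size, SD, effect size, power or allocation ratio, so there is no figure of the plan to reproduce. Assumptions: a 2×2 layout (population × arm), equal cells of n people, a common SD *s* of the change score, and two-sided 0.05 (the SAP gives 0.05 but not the sidedness). I show n = 5 to 20.

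**Standard errors.**
- Synbiotic minus placebo in one population: √(s²/n + s²/n) = s√(2/n).
- Overall, the mean of the two population differences: √[¼(2s²/n + 2s²/n)] = s√(1/n).
- One-arm change from baseline: s/√n.
- Arm-by-population interaction: √(2s²/n + 2s²/n) = s√(4/n).

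Overall against per-population: √(1/n) ÷ √(2/n) = 0.707 at any n. The variance is halved and the standard error is 29% smaller. Overall against one-arm: the ratio is 1, so there is no gain in standard error.

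**95% half-widths (t × SE, in units of s) and noncentral-t power for a common effect of 0.8 s.** Degrees of freedom are 2n−2 per population, 4n−4 overall and n−1 for one arm.

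| n per cell | Half-width, per population | Half-width, overall | Half-width, one-arm change | Power, per population | Power, overall |
|---|---|---|---|---|---|
| 5 | 1.46 | 0.95 | 1.24 | 0.20 | 0.39 |
| 10 | 0.94 | 0.64 | 0.72 | 0.40 | 0.69 |
| 15 | 0.75 | 0.52 | 0.55 | 0.56 | 0.86 |
| 20 | 0.64 | 0.45 | 0.47 | 0.69 | 0.94 |

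For a common effect of 1 s at n = 10, power is 0.56 per population and 0.87 overall. Two independent per-population tests then give significance in exactly one population with probability 2 × 0.56 × 0.44 = 0.49.

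**Unequal populations.** If one population supplies a fraction f of the sample, the per-population standard error is √(1/f) times that of the precision-weighted overall estimate. With a 30:70 split this is √(1/0.3) = 1.83 in the smaller population and √(1/0.7) = 1.20 in the larger.

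**When effects differ.** Let the effects be δ and kδ. The overall z is [(1+k)δ/2] ÷ (s/√n), and the z in the better-responding population is δ ÷ (s√(2/n)). Their ratio is (1+k)/√2, which reaches 1 at k = √2 − 1 = 0.41. If only one population responds (0.8 s, n = 10), power is 0.40 there and 0.23 overall. With equal and opposite effects the overall effect is zero and power is 5%.

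**The case against.** Four objections have force.

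1. The Design section aims at differing effects between the populations, which is an interaction question. Population-specific reporting serves that aim, and the Objective can be read as effects in each population. This stands: separate results are legitimate, and the overall contrast is an addition.

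2. A reader might infer that no overall effect was planned and that the conclusions rest on half-sample tests. The documents do not show that. The two-way ANOVA has unnamed factors and could include an arm effect across populations. The Results section presents itself as a selection of the main results, and the cortisol and ACTH sentence does not say which test lies behind it. What can be said is that the contrast is not specified and not reported.

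3. A reader might also infer that the overall estimate would be far more precise than the tests reported. Most reported positive findings are one-arm changes, on about a quarter of the sample if cells are equal, and their standard error equals that of the overall contrast. Only degrees of freedom are gained (half-width 0.72 against 0.64 at n = 10). The 29% applies against a placebo contrast within one population. The one-arm tests do not estimate the effect against placebo at all; that is a separate and more serious defect, and repairing it only within populations would leave the loss described here.

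4. The overall mean can hide opposite responses. Results reports different responses by population for IL-1β (up in sedentary people, slightly down in players) and for CRH (down in sedentary people, where placebo recipients also fell, and slightly up in athletes). It also reports that training changed the response for dopamine and anxiety. Inferring absence of effect from a non-significant overall mean would therefore be unsafe, and at n = 5 to 20 its interval still spans ±0.95 to ±0.45 SD.

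**Conclusion.** The point holds as a gap in specification and reporting. The SAP does not name the ANOVA factors or an overall randomised contrast, and the Results give no overall estimate or interval, even for depression, where both populations moved the same way. Relative to a per-population placebo contrast, the overall contrast halves the variance; at n = 10 per cell, power for a common 0.8 SD effect rises from 0.40 to 0.69. This rests on equal cells, a common SD and a common effect, with all sizes assumed. The advantage disappears when the weaker population's effect is below about 41% of the stronger one's. The change is a cheap improvement; it does not show that any reported finding is wrong.

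**What to change.** For each outcome, fit one model of the final value (or the change) with arm, population, arm-by-population and baseline, and name these terms in the SAP. Report:

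- the synbiotic-minus-placebo difference with its 95% interval, overall and adjusted for population, stating how the populations are weighted;
- the same difference with its interval within each population;
- the interaction test, which serves the Design aim.

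Describe an effect as shared by both populations from the overall contrast only when the interaction and the population-specific estimates do not contradict it. Report cortisol, ACTH, IgA, norepinephrine and the metabolic profile through the overall and per-population intervals, and do not conclude absence of effect from a non-significant test. Because results are already in the document, label any contrast that was not specified beforehand as added afterwards.

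The cost is a few sentences in the SAP and a re-analysis of existing data.

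### The claim of no appreciable metabolic effect rests on non-significance and normal-range values, with no between-arm estimate, interval or margin to support it

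*Combined protocol and SAP*

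**What the plan says.** The Design section describes a "triple blinded, randomized, placebo-controlled pilot study" in sedentary people and soccer players, tested at baseline and again after 30 days of supplement or placebo.

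The Statistical Analysis Plan section is one short paragraph. It gives a Shapiro-Wilk check and a two-way repeated ANOVA, "followed by Student's paired and unpaired t-tests to analyze the intervention effect". On reporting it says "The values were expressed as mean" ± SD, with significance at p<0.05. It does not say which contrast the unpaired t-test addresses.

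The Results section introduces "blood concentrations of glucose, cholesterol, and triglycerides as measurements of metabolic profile", notes that both populations had normal lipid and glycaemic levels, and concludes from this, as something expected, that "the consumption of the synbiotic did not provoke an appreciable or significant effect". No mean, SD, p-value or interval is printed for these three outcomes.

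Elsewhere in the Results, null findings are worded as test outcomes, for example "There were no significant differences in levels of cortisol and ACTH between groups or as a consequence of the intervention". Salivary IgA and norepinephrine are treated in the same way.

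**The concern.** The metabolic sentence makes two claims: the effect was not significant, and it was not appreciable. The planned tests can support the first. The second needs three things: an estimate of the synbiotic-minus-placebo difference, its precision, and a statement of what size would count as appreciable. Neither the plan nor the Results text supplies any of them.

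The normal-range argument does not fill the gap. It describes where the values lie, not how much the synbiotic moved them relative to placebo. Two arms can both lie inside a reference range and still differ.

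At stake is an inconclusive result for three outcomes being read as a negative one. The study calls itself a pilot, so a reader may well want the size and precision of each effect, and significance verdicts supply neither.

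**Working it through.** **Is there a figure to reproduce?** No. The documents state no sample size, allocation ratio, SD, pre-post correlation, power, effect size or margin. The actual interval therefore cannot be computed, and what follows is an illustration under stated assumptions.

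**Inputs**
- Significance level 0.05, from the Statistical Analysis Plan section. Sidedness is not stated; two-sided is assumed.
- n per arm within one population: assumed 10, 15, 20 and 30, with 1:1 allocation.
- Pre-post correlation r: assumed 0, 0.5, 0.7 and 0.8.
- Common SD within arms: set to 1, so results are in SD units.

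**Formula.** For the baseline-adjusted difference between arms,

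half-width = t(0.975, 2n−3) × √(2/n) × √(1−r²).

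**Worked ends of the range**
- n=10, r=0: 2.110 × 0.4472 × 1 = 0.94 SD.
- n=30, r=0.8: 2.002 × 0.2582 × 0.6 = 0.31 SD.

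**Full grid (± SD)**

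| n per arm | r=0 | r=0.5 | r=0.7 | r=0.8 |
|---|---|---|---|---|
| 10 | 0.94 | 0.82 | 0.67 | 0.57 |
| 15 | 0.75 | 0.65 | 0.54 | 0.45 |
| 20 | 0.64 | 0.55 | 0.46 | 0.38 |
| 30 | 0.52 | 0.45 | 0.37 | 0.31 |

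**Reading the grid.** If the estimate were exactly zero, the interval would still contain a difference of 0.5 SD in 10 of the 16 cells: all four at n=10, three at n=15, two at n=20 and one at n=30. In the other six it would exclude 0.5 SD. The count describes this grid only and is not a probability.

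A non-significant estimate need not be zero. One just short of significance has an interval reaching almost twice the half-width, for example nearly 2 × 0.31 = 0.62 SD in the most favourable cell. Without the estimate, the reader cannot tell which case applies.

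**Cross-check without baseline adjustment.** With t(0.975, 2n−2) × √(2/n), the half-width is ±0.94, ±0.75, ±0.64 and ±0.52 SD at 10, 15, 20 and 30 per arm. Two-sided t-test power for a true 0.5 SD difference is about 19% at 10 per arm, 34% at 20 and 48% at 30. About 63 per arm would be needed for 80% (normal approximation).

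**The case against.** **A null p-value in this study can never exclude half an SD.** A reader might infer this, but the documents do not support it. Both n and r are unknown. With r=0.8 and 15 or more per arm, or r=0.5 and 30 per arm, an interval centred near zero would exclude half an SD. The statement is conditional.

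**The same fault runs through all the null findings.** A reader might extend the criticism to IgA, cortisol, ACTH and norepinephrine. Their wording reports only that differences or changes were not significant, which is a correct description of a test. Among these outcomes, only the metabolic sentence adds a claim about size.

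**No estimates exist behind the conclusion.** This too goes further than the text allows. The plan says values were summarised as mean ± SD, and the Results are a selective narrative that may have been written around tables. What can be said is that no estimate or interval is printed for these outcomes and no between-arm estimate is planned.

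**Arm SDs are enough.** This stands in part. With n, the final-visit SDs do give the standard error of the unadjusted difference in final values. The pre-post correlation is needed only for change or baseline-adjusted contrasts. However, n is not given, and the plan does not say that the unpaired t-test compares synbiotic with placebo.

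**The consequence is small.** This also stands in part. The metabolic outcomes are not labelled primary (no outcome is), and no safety or equivalence claim is built on the sentence. The stated aim is to identify possible differing effects; planning a later study is not mentioned.

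**The study is finished.** True, so any interval or margin added now is post hoc and must be labelled as such. The analysis needs only data already collected.

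**Conclusion.** The point holds for the sentence on glucose, cholesterol and triglycerides. It makes a claim about effect size that neither the planned tests nor the normal-range values can carry, and this is so at any sample size, because no between-arm estimate, interval or margin is given.

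How much the data leave open depends on n and r, both assumed here. Across 10 to 30 per arm and r from 0 to 0.8, the half-width runs from about ±0.94 to ±0.31 SD. Many but not all of these combinations leave half an SD open when the estimate is near zero.

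The remaining null findings named above lack an interval but are not misworded. The correction should be made, since it changes what may be concluded, but it concerns outcomes that are not designated primary.

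**What to change.** 1. Report each outcome as the baseline-adjusted synbiotic-minus-placebo difference with its 95% CI, separately for sedentary people and athletes. Label this as a post hoc addition to the analysis plan, and state n per arm beside it.
2. Reword the metabolic sentence to say that no significant difference was detected, followed by the estimate and interval. Do not use normal-range values as evidence on the size of the effect.
3. Say that an effect was not appreciable only if the interval excludes a stated margin, and label that margin post hoc. Otherwise call the result inconclusive.
4. For IgA, cortisol, ACTH and norepinephrine, add the interval; the wording can stay.

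The cost is a short addition to the plan and one extra output column from data already held. The null claims become weaker.
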